### **5.5.2      Sponsor Follow-Up**

For serious adverse events and pregnancies, the Sponsor or a designee may follow up by telephone, fax, electronic mail, and/or a monitoring visit to obtain additional case

details and outcome information (e.g., from hospital discharge summaries, consultant reports, autopsy reports) in order to perform an independent medical assessment of the reported case.

## **5.6 POST-STUDY ADVERSE EVENTS**

The Sponsor should be notified if the investigator becomes aware of any serious adverse event that occurs after the end of the adverse event reporting period (defined as 28 days after the last dose of study drug), if the event is believed to be related to prior study drug treatment.

The investigator should report these events directly to the Sponsor or its designee, either by faxing or by scanning and emailing the Serious Adverse Event/Adverse Event of Special Interest Reporting Form using the fax number or email address provided to investigators.

## **5.7 EXPEDITED REPORTING TO HEALTH AUTHORITIES, INVESTIGATORS, INSTITUTIONAL REVIEW BOARDS, AND ETHICS COMMITTEES**

The Sponsor will promptly evaluate all serious adverse events and adverse events of special interest against cumulative product experience to identify and expeditiously communicate possible new safety findings to investigators, IRBs, ECs, and applicable health authorities based on applicable legislation.

To determine reporting requirements for single adverse event cases, the Sponsor will assess the expectedness of these events using the Olesoxime Investigator's Brochure.

The Sponsor will compare the severity of each event and the cumulative event frequency reported for the study with the severity and frequency reported in the applicable reference document.

Reporting requirements will also be based on the investigator's assessment of causality and seriousness, with allowance for upgrading by the Sponsor as needed.

## **6. STATISTICAL CONSIDERATIONS AND ANALYSIS PLAN**

### **6.1 ANALYSIS POPULATIONS**

#### **Safety Population**

The safety population will consist of all patients who received at least one dose of study medication. All safety data will be summarized based on the safety population.

## **Intent-To-Treat Population**

The intent-to-treat (ITT) population will include all patients who received at least one dose of study medication and have at least one post-baseline assessment of MFM. The ITT population will be the primary population for the efficacy analysis.

As this is an open-label study no formal hypothesis testing will be performed. Data will be summarized using descriptive statistics and will be compared with natural history data. Further details will be provided in the statistical analysis plan (SAP).

## **6.2 DETERMINATION OF SAMPLE SIZE**

The sample size will be determined by the number of patients who participated in studies TRO19622CLEQ1275-1 and/or TRO19622CLEQ1115-1 and who meet the enrolment criteria. The primary objective of the study is to assess the safety and tolerability of olesoxime.

## **6.3 HISTORICAL DATA**

Descriptive statistics will be used to describe the disease course of patients from the last visit of Studies TRO19622CLEQ1275-1 and TRO19622CLEQ1115-1 and the start of current study BN29854. Further exploratory analyses will be described in a separate SAP.

## **6.4 SUMMARIES OF CONDUCT OF STUDY**

Descriptive statistics will be used to evaluate the conduct of the study. Patient disposition, compliance with medication and major protocol deviations will be assessed.

## **6.5 SUMMARIES OF TREATMENT GROUP COMPARABILITY**

Demographic data collected at screening and baseline characteristics will be summarized. Summaries will be presented overall and by the treatment received in the previous study.

Summaries will be based on the safety population.

Where available, similar descriptive statistics may be provided for the natural history data.

## **6.6 PRIMARY ANALYSES**

Safety analysis will be based on the safety population.

Safety variables (e.g., laboratory tests, vital signs, and ECG) will be summarized for each assessment time (including follow-up) using descriptive statistics. *The data will be summarized by the dose being taken at the time of the assessment (10 mg/kg QD or 10 mg/kg BID). Data from the two 24-hour Holter ECG assessments will also be summarized.*

Adverse events will be coded and summarized by body system and preferred term. Adverse events will also be summarized by intensity and relationship to trial treatment as assigned by the investigator. Serious adverse events will be summarized separately. *Adverse events will be summarized by the dose being taken at the onset date of the adverse event.*

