## **6.7           SECONDARY ANALYSES**

The change from baseline in MFM D1+D2 and MFM Total Score will be summarized at each visit using descriptive statistics. *The data will be summarized by the dose being taken at the time of the assessment.* Mean changes and 95% confidence intervals over time will be presented graphically. Summary statistics by age and SMA type will also be provided.

Where available, similar descriptive statistics may be presented for the Natural History Data.

Statistical modelling approaches may be used to explore the effects of differences in baseline covariates. Details will be provided in the SAP.

The incidence of disease associated medical complications and procedures will be summarized. *The data will be summarized by the dose being taken at the onset date of the event.*

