2.1.3 Exploratory Efficacy Outcome Measures

Exploratory outcome measures include:

- Forced vital capacity (FVC)
- MFM D1+D2 responder rates, where a responder is defined as no worsening from baseline in the MFM D1+D2 score
- Hammersmith functional motor scale (HFMS) [before removal from schedule of assessments as of protocol version 3]

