3. STUDY CONDUCT

3.1 RANDOMIZATION

BN29854 is a single arm, open-label study, and all patients receive olesoxime at 10mg/kg q.d.

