4.4.2.4 SMA Related Medical Complications and Procedures

SMA related medical complications and procedures will be collected through the adverse event (AE) reporting of the study and through the reporting of on-study SMA related surgeries and procedures. Events will be identified by applying a prospectively defined basket of MedDRA lowest level terms to the AE dataset and to the on-study SMA related surgery and procedure dataset.

For each event recorded, the term entered by the investigator describing the event (the 'verbatim term') will be assigned to a standardized term (the 'lowest level term') based on the most up-to-date version of MedDRA. Data displays of SMA related medical complications and procedures will be performed using the system organ class and lowest level terms. For summaries of event incidences, patients who experience the same event on more than one occasion will be counted once in the calculation of the event frequency at the highest intensity reported. Each table will also present the number and percentage of patients who experience at least one SMA related medical

complication or procedure during the study (including safety follow-up period) and the total number of events reported.

On-study SMA related surgeries and procedures which have not been identified by the MedDRA basket will be summarized separately.

Similar analyses will be performed for SMA related medical complications occurring in the NatHis-SMA comparison population. The pre-specified MedDRA basket will be applied to the AE dataset for this population, and the data will be summarized as described for the ITT population. AEs which have not been identified by the MedDRA basket and have been classified as 'due to the disease' by the investigator will also be summarized.

The AE rate adjusted for patient years (all occurrences, by lowest level term) and corresponding exact 95% CIs for the event rate in the ITT and NatHis-SMA comparison populations will also be presented. The event rate per 100 patient-years is computed as follows:

$$\text{AE rate} = (\text{number of AEs observed} / \text{total patient-years at risk}) * 100$$

where for study BN29854

Total patient-years at risk = sum across all patients of the time intervals (in years) between start of study therapy up to 28 days after study withdrawal/completion

and for the NatHis-SMA study

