4.6.1 Exposure to Study Medication

The following extent of exposure to study drug will be summarized:

Olesoxime—F. Hoffmann-La Roche Ltd
20/Statistical Analysis Plan BN29854

- Duration of treatment and number of interruption days
- Extent of compliance to the prescribed treatment

The duration of total treatment intake will be calculated from the first day of study medication to the last day of study treatment:

Duration of treatment = date of the last dose – date of the first dose + 1 day

The percentage of compliance over the entire treatment period will be calculated as:

Compliance = total number of days under treatment * 100 / duration of treatment

The number and percentage of patients with overall compliance < 80% and ≥ 80% will be summarized.

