4.6.2 Adverse Events

For each adverse event (AE) recorded, the term entered by the investigator describing the event (the 'verbatim term') will be assigned to a standardized term (the 'preferred term') based on the most up-to-date version of MedDRA. Data displays of AEs will be performed using the system organ class and preferred terms. For summaries of AE incidences, patients who experienced the same event on more than one occasion will be counted once in the calculation of the event frequency at the highest intensity reported. Each table will also present the overall number of patients experiencing at least one AE and the total number of AEs reported.

AEs will be summarized for the following analysis periods separately:

Treatment period: includes (a) the AEs for which the onset date is on or after the first day of the study drug up to 28 days after the last dose day; or (b) the AEs for which the onset date is prior to the first dose day with the end date on or after the first dose day or the AE is unresolved, and the most extreme intensity is greater than the initial intensity.

Overall AEs, AEs reported in ≥ 5% of patients, AEs by intensity, AEs leading to death, serious AEs (SAEs), AEs leading to withdrawal of study treatment, AEs leading to dose modification or interruption, AEs related to study treatment (as assigned by the treating investigator), and SAEs related to study treatment will be summarized. SAEs reported in ≥ 1% of patients may also be summarized.

Follow-up period: includes the serious AEs for which the onset date is 29 days or more after the last dose day and that the investigator believes to be related to prior study drug treatment.

In addition, non-treatment emergent AEs, including the SAEs caused by a protocol-mandated intervention (e.g. invasive procedures such as biopsies, discontinuation of

medications) for which the onset date is before the date of the start of study medication, will be listed.

The following rules will be applied for AEs with missing onset and/or end dates:

- Events that are missing both onset and end dates will be considered treatment emergent, given that a patient had at least one dose of study drug.
- If the onset date is missing and the end date is on or after the first dosing date, then the event will be considered treatment emergent.
- If the end date is missing and the onset date is on or after the first dosing date, then the event will be considered treatment emergent.

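### Adverse events are to be split by dose at onset, but the supplied SAP has no exposure or patient-year rate by dose, so unequal QD and BID time can hide or create a difference

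*Protocol*

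**What the plan says.** **Protocol Version 4.** Section 6.6 requires: "Adverse events will be summarized by the dose being taken at the onset date of the adverse event". Section 6.7 requires the same for disease-associated complications and procedures: "The data will be summarized by the dose being taken at the onset date of the event". Neither names a metric, a denominator or an exposure measure. Section 6.1 leaves further detail to the SAP and plans no formal testing.

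**SAP.**
- Section 3.1 states that "all patients receive olesoxime at 10mg/kg q.d", and Section 2 describes the study in the same way. The latest protocol version it mentions is 3, where it refers to the HFMS "before removal from schedule of assessments as of protocol version 3" (Section 2.1.3).
- Section 4.6.2 counts patients: "patients who experienced the same event on more than one occasion will be counted once in the calculation of the event frequency". Each table adds the total number of AEs. No patient-years enter.
- Section 4.6.1 gives one span per patient: "The duration of total treatment intake will be calculated from the first day of study medication to the last day of study treatment". It is not divided by dose.
- Section 4.4.2.4 has the only patient-year rate: "The AE rate adjusted for patient years (all occurrences, by lowest level term"). It covers SMA related complications in the ITT and NatHis-SMA populations. Each treated patient contributes one risk time, "between start of study therapy up to 28 days after study withdrawal/completion", pooled over doses.

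**The concern.** The design makes time on QD and time on BID unequal. The study began on QD (Protocol 1.3). Consenting patients move to BID at a visit whose date varies by patient, and those who do not consent remain on QD (Protocol 3.1.1.4). Follow-up ends on commercial availability, local regulation or sponsor decision, within a cap of 4 years after the last enrolment, or after a fixed 3 years in the UK (Protocol 3.2). Nothing equalizes the two periods.

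The percentage of patients with an event and the total number of events both grow with time observed. If the counting rule in SAP 4.6.2 is applied by dose, the two columns reflect time as well as dose. The denominator of each column is also undefined: SAP 4.1.2 fixes the analysis set but not who counts as treated at each dose.

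Safety is the primary objective (Protocol 2.1), and this is the planned AE display that separates the doses. With no test planned, readers are likely to compare the columns by eye.

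**Working it through.** The documents give no target, power or precision for a comparison of doses, so there is no plan figure to reproduce. The check is whether the stated counting rule gives comparable columns when time differs.

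**Inputs**
- Background SAE frequency: 34 patients (31.5%) on olesoxime in the earlier 24-month study (Protocol 1.2.2). The implied arm sizes are consistent: 34/108 = 31.5%, 29/57 = 50.9%, and 63/165 = 38.2%.
- Time on QD and on BID: **not given**. The values below are assumptions chosen to show direction.
- Model: constant hazard of a first SAE.

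**Step 1. Hazard.** λ = −ln(1 − 0.315)/2 = 0.189 first SAEs per year.

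**Step 2. Crude percentage.** P(t) = 100 × (1 − exp(−rate × t)).

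| True BID rate | QD time | BID time | QD column | BID column |
|---|---|---|---|---|
| same as QD | 2 y | 0.5 y | 31.5% | 9.0% |
| same as QD | 1 y | 2 y | 17.2% | 31.5% |
| twice QD | 2 y | 1 y | 31.5% | 31.5% |

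The first two rows create a difference that is not there, in opposite directions. The third hides a doubling completely.

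**Step 3. When a difference vanishes.** With a BID rate k times the QD rate, the columns are equal when kλ × (BID time) = λ × (QD time), that is, when BID time = QD time / k. This does not depend on λ.

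**Step 4. Sensitivity to the background rate.** With 50.9% at 24 months (the earlier placebo arm), λ = 0.356 per year. Rows 1 and 3 become 50.9% against 16.3%, and 50.9% against 50.9%. The pattern is unchanged.

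**Step 5. Dividing by time.** First SAEs per 100 patient-years at risk are 100 × 0.189 = 18.9 on both doses in rows 1 and 2, and 18.9 against 37.8 in row 3. The distortion from unequal time is gone.

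**Step 6. The existing pooled rate.** For SMA complications, a BID rate twice the QD rate with q years on QD and b on BID gives a pooled rate of (q + 2b)/(q + b) times the QD rate. For q = 2 and b = 1 this is 4/3 = 1.33. The pooled figure dilutes the difference and does not provide the split that Protocol 6.7 requires.

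**The case against.** **The SAP may simply be out of date.** It reads as written before Version 4, so it lacks every by-dose summary, and a later SAP may exist. This stands. A reader might infer that the sponsor chose crude by-dose columns. The documents do not support that: Protocol 6.6 names no metric and does not exclude rates, and no document states that SAP 4.6.2 will be applied by dose. They show a by-dose requirement whose only available counting rule, if followed, gives columns that are not comparable.

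**Comparing doses is not an objective.** Protocol 2.1 asks for the nature, frequency and severity of AEs, without testing. This limits the severity. But Version 4 chose to split AEs by dose, and frequency by dose cannot be read without time on each dose.

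**Rates would still not isolate the dose effect.** This is correct. BID follows QD in anyone who had both, and patients choose BID. Rates remove only one avoidable distortion.

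**Other safeguards exist.** The Holter recordings and 4-week blood sampling (Protocol 3.1.1.4 and 4.4.9.1) are short-term checks. The exposure-response work in Protocol 6.9 includes AEs but is exploratory and reported outside the clinical study report. Neither gives AE frequency over time on each dose.

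**The exposure times are assumed.** This stands in full. A reader might infer from the figures that the bias has a known size, or that BID will look safer than it is. Neither follows; the direction depends on times that the documents do not give.

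**Conclusion.** The point holds and should be fixed before the by-dose safety tables are produced. Protocol Version 4 requires AEs and SMA complications by dose at onset. The supplied SAP provides no time on each dose, no denominator for each dose column and no patient-year AE rate by dose. Sequential dosing with individual switch times and open follow-up means that time on QD and BID will differ.

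Only the mechanism is established. The illustrated sizes rest on a constant hazard borrowed from the earlier study and on assumed durations. The conclusion is conditional on no later SAP having closed the gap.

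**What to change.** Update the SAP for the QD/BID structure, or point to a later version that already does this:

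1. Summarize patients treated, treatment duration and patient-years by dose.
2. Within the safety population, use patients with at least one dose at that level as the denominator of each dose column.
3. Add rates per 100 patient-years, by dose at onset, for all AEs, SAEs, and AEs leading to dose modification, interruption or withdrawal. The formula in SAP 4.4.2.4 can be reused, with person-time covering the same window as the AEs counted: up to 28 days after the last dose (Protocol 5.3.1, SAP 4.6.2), with that tail assigned to the last dose taken. Use confidence intervals that allow for repeat events within a patient.
4. Split the SMA complication rate in SAP 4.4.2.4 by dose in the same way, to meet Protocol 6.7.
5. Keep the crude table, and state beside it that the rates correct only for time at risk, not for dose order, ageing, concomitant therapy or self-selection into BID.

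The cost is SAP wording and a few extra tables. Study drug administration is already recorded in the eCRF (Protocol 4.2.2.1), so no new data or visits are needed.

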#### **5.3.5.1 Diagnosis versus Signs and Symptoms**

A diagnosis (if known) should be recorded on the Adverse Event eCRF rather than individual signs and symptoms (e.g., record only liver failure or hepatitis rather than jaundice and elevated transaminases). However, if a constellation of signs and/or symptoms cannot be medically characterized as a single diagnosis or syndrome at the time of reporting, each individual event should be recorded on the Adverse Event eCRF. If a diagnosis is subsequently established, all previously reported adverse events based on signs and symptoms should be nullified and replaced by one adverse event report based on the single diagnosis, with a starting date that corresponds to the starting date of the first symptom of the eventual diagnosis.

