### **5.3.5.3 Persistent or Recurrent Adverse Events**

A persistent adverse event is one that extends continuously, without resolution, between patient evaluation timepoints. Such events should only be recorded once on the Adverse Event eCRF. The initial severity (intensity or grade) of the event will be recorded at the time the event is first reported. If a persistent adverse event becomes more severe, the most extreme severity should also be recorded on the Adverse Event eCRF. If the event becomes serious, it should be reported to the Sponsor immediately (i.e., no more than 24 hours after learning that the event became serious; see Section 5.4.2 for reporting instructions). The Adverse Event eCRF should be updated by changing the event from "non-serious" to "serious," providing the date that the event became serious, and completing all data fields related to serious adverse events.

A recurrent adverse event is one that resolves between patient evaluation timepoints and subsequently recurs. Each recurrence of an adverse event should be recorded as a separate event on the Adverse Event eCRF.

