### **5.3.5.8      Preexisting Medical Conditions**

A preexisting medical condition is one that is present at the screening visit for this study. Such conditions should be recorded on the General Medical History and Baseline Conditions eCRF.

A preexisting medical condition should be recorded as an adverse event only if the frequency, severity, or character of the condition worsens during the study. When recording such events on the Adverse Event eCRF, it is important to convey the concept that the preexisting condition has changed by including applicable descriptors (e.g., "more frequent headaches").

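### A persistent adverse event that starts on QD and worsens or becomes serious on BID is shown only under QD in the by-dose adverse event tables

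*Protocol*

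**What the plan says.** Three rules act together.

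- **Attribution.** Protocol 6.6 gives one criterion for the by-dose tables and no exception: "Adverse events will be summarized by the dose being taken at the onset date of the adverse event".
- **Recording.** Protocol 5.3.5.3 says of persistent events: "Such events should only be recorded once on the Adverse Event eCRF". On worsening it says: "If a persistent adverse event becomes more severe, the most extreme severity should also be recorded on the Adverse Event eCRF". A later change to serious is made on that same record, "providing the date that the event became serious, and completing all data fields related to serious adverse events". That section asks for no date of an increase in intensity.
- **Worsening after exposure starts.** SAP 4.6.2(b) brings an event that began before the first study dose into the treatment period if it was still present at or after that dose "and the most extreme intensity is greater than the initial intensity". The rule applies at the first dose of study drug only.

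SAP sections 2 and 3.1 describe QD dosing for all patients, so the SAP has no by-dose adverse event table and no rule for the change from QD to BID.

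**The concern.** Safety is the primary objective (Protocol 2.1). Version 4 raises the regimen from 10 mg/kg QD to 10 mg/kg BID, with AUC projected to rise by about 100% (Protocol 3.3.1). Patients who switch are already on QD, and Protocol 1.4 describes a high background of comorbidity, so some events will be ongoing at the switch.

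If an ongoing event gets worse at the higher dose, the by-dose tables place the worse grade or the seriousness under the lower dose. For these events the displacement always goes the same way: the BID column shows too little and the QD column too much. There is no independent data monitoring committee (Protocol 3.3, SAP 3.2), so these tables are a main place where a reader would look for a difference between the doses.

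**Working it through.** The plan states no figure that depends on this rule, so the check follows one event through the rules.

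**Inputs.** One onset date per persistent event, with later worst severity and seriousness added to the same record (Protocol 5.3.5.3); dose column set by onset date (Protocol 6.6); worsening rule only at the first study dose (SAP 4.6.2).

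**Test event.** Mild and non-serious on QD, ongoing at the first BID dose, then severe and serious on BID.

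| Count | As written: QD | As written: BID | With a worsening rule at first BID dose: QD | With a worsening rule at first BID dose: BID |
|---|---|---|---|---|
| Any event | 1 | 0 | 1 | 1 (flagged worsened) |
| Severe | 1 | 0 | 0 | 1 |
| Serious | 1 | 0 | 0 | 1 |

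**Effect on the difference, BID minus QD.**

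- Severe or serious: as written 0 − 1 = −1; with the rule 1 − 0 = +1. The shift is 2 per event, or 2k for k such events.
- Any event: as written 0 − 1 = −1; with the rule 1 − 1 = 0. The shift is 1 per event, or k.

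The documents do not give k. For assumed values k = 1, 3 and 5, the severe or serious difference is too low by 2, 6 and 10.

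**Which intensity is tabulated.** The SAP sentence on highest intensity is written for patients who have the same event more than once. It does not say which severity of a single persistent record is used. The table above takes the most extreme severity, the natural reading because no rule cuts the record at the switch. If the initial severity were used instead, the severe grade would appear in neither column. The BID column is empty either way.

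**Can SAP 4.6.2(b) be copied as it stands?** Not quite. It compares initial with most extreme intensity and uses no date of worsening. Applied unchanged at the switch, it would also count as BID-worsened an event that had already worsened on QD and was still ongoing. A date is needed to separate the two.

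**A related route.** When a diagnosis replaces symptoms, Protocol 5.3.5.1 records it "with a starting date that corresponds to the starting date of the first symptom of the eventual diagnosis". A diagnosis made on BID whose first symptom fell on QD is therefore also placed under QD. It acts in the same direction and is not included in k.

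**The case against.** **Onset-date attribution is a simple and defined convention.** True, and it should stay. But the SAP pairs it with a worsening rule at the first exposure, and Version 4 added a second change of exposure without one.

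**Worsening on BID need not be caused by BID.** This stands. A reader might infer that the tables credit BID toxicity to QD. The documents do not support that: SMA is progressive (Protocol 1.1), and BID always follows QD in time, so some worsening would occur anyway. The defect is only that the tables cannot show it under BID.

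**Much of the safety picture is unaffected.** This also stands. A recurrence on BID is captured: "Each recurrence of an adverse event should be recorded as a separate event on the Adverse Event eCRF". Severe or serious secondary events can be recorded separately (Protocol 5.3.5.2). Laboratory tests, vital signs and ECG are summarized by dose at assessment, and both Holter recordings are summarized (Protocol 6.6). Events that become serious are reported to the sponsor within 24 hours. A reader might infer that BID harm in general is hidden; the gap is confined to persistent, single-record events in the by-dose adverse event tables.

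**No formal QD–BID comparison is planned.** Correct: the summaries are descriptive (Protocol 6.1). The columns will still be read side by side, and a misplaced event misleads without a test.

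**The protocol's own rules might seem to call for a second eCRF record.** They do not. Protocol 5.3.5.8 makes a condition already present at screening an adverse event "only if the frequency, severity, or character of the condition worsens during the study", and SAP 4.6.2(b) reclassifies an existing record. A second record would conflict with the record-once rule; a counting rule is the true parallel.

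**The eCRF may already capture a date of severity change.** Possible. The eCRF and its completion guide are not among the documents; the protocol text does not ask for one.

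**Conclusion.** The point holds for persistent events recorded once. With onset on QD and an increase in intensity or seriousness after the first BID dose, the event is shown only under QD, and its BID-period worsening is not visible in the by-dose adverse event tables. Each event that first becomes severe or serious on BID lowers the BID-minus-QD difference in that count by 2. The total cannot be computed without the number of events ongoing at the switch. The intensity part assumes that the most extreme severity on the record is tabulated; the seriousness part needs no such assumption, because the record itself is changed. The point does not invalidate the study, but it misplaces events in the primary safety tables and should be corrected.

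**What to change.** Keep the single eCRF record and the onset-based table. Add to Protocol 6.6 and SAP 4.6.2:

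- An event with onset on QD that increases in intensity or becomes serious on or after the first BID dose is also counted as BID-emergent, at its BID-period intensity or seriousness, and flagged as worsened rather than new.
- The QD column shows the worst intensity and seriousness reached before the first BID dose.
- Worsened events are shown separately from new-onset BID events.

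Use the date of the first BID dose, not of the dose increase visit: Protocol 3.1.1.4 starts BID on the day after the Holter monitor is removed. Use the date of becoming serious, which is already collected. Record the date of intensity worsening prospectively, and query it for events already entered that were ongoing at the switch. State in advance how events with no recoverable date are shown. The SAP must in any case be updated for the dose increase.

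Cost: one analysis rule, one date field or completion instruction, and queries limited to events ongoing at the switch. Downside: a worsened event appears in both dose columns, and natural progression after the switch will add some events to BID, which is why they should be displayed apart from new-onset events.
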